- Full-time employed
- Part-time/casual employment
- Unemployed
- Home Duties
- Retired
- Student
- Other

Please specify

BLOOD TESTS

YES NO

Has a fasting blood sample been taken to measure serum fatty acids?

Has a fasting blood sample been taken for FBC, MBA, CRP, fasting lipids (HDL, TGC, LDL)

Has a serum pregnancy test been taken (if subject male, tick No box)

PHYSICAL EXAMINATION/VITAL SIGNS

Height (without shoes)	cms
Weight (without shoes, with clothes)	kgs
Blood Pressure (sitting, after resting for 5 minutes)	mmHG

Site Number:

Randomisation Number:

Subject Initials:

Study Selected Knee:

STUDY FISH OIL	
	YES NO
Has the Visit 7 fish oil been returned (inc. all empty bottles)	 
How many mLs are remaining?mL	
What percentage of expected was taken?% (=amount actually taken/amount expected to be taken x 100)	
We want at least 75% compliance so if necessary, encourage subject to keep taking the fish oil on a daily basis	

ANALGESIC MEDICATION	
Number of Paracetamol tablets supplied at previous visit	
Number of Paracetamol tablets returned	
Number of paracetamol tablets accounted for in diary	
Difference between number of tablets recorded taken and actual number of tablets removed from package.	
Remember to remind Subject the importance of returning the empty foil strips. Remember to record these details in the Analgesic Medication Record	

VISIT 7 DIARY	
	YES NO
Has the subject's Visit 7 diary been collected and reviewed	 
Have all diary concomitant medication records been transcribed into the CRFs Concomitant Medication Section	 
Have all diary adverse event records been transcribed into the CRFs Adverse Events Section	 

Site Number:

Randomisation Number:

Subject Initials:

Study Selected Knee:

FINALISING THE STUDY		
	YES	NO
Has an appointment been made for the subjects final DEXA scan on their study selected knee? Details:/...../.....am/pm DD/MM/YYYY		
Has an appointment been made for the subjects final MRI on their study selected knee? Details:/...../.....am/pm DD/MM/YYYY		
Has an appointment been made for the subjects x-ray on their study selected knee? Details:/...../.....am/pm DD/MM/YYYY		
Has the subject been sincerely thanked for their time, effort and cooperation during the study?		
Has the pedometer that was issued to the subject at their last visit been returned? Please record all details in the Pedometer Record Section of the CRF		
Has the subject's Hospital records been updated to show that they have completed/withdrawn from the study?		
Has a letter been sent to the subject's GP to notify their Dr of their completion/withdrawal from the study?		

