SUPPLEMENTARY FILE 1: Study Protocol for Fish oil in knee osteoarthritis: A randomised clinical trial of low dose versus high dose (also known as the FOSTAR study).

[figure not shown]
STUDY DESIGN

The FOSTAR study is a randomised double-blind controlled clinical trial of 200 subjects with symptomatic knee osteoarthritis from three Australian centres (The Queen Elizabeth Hospital, Adelaide, South Australia; Menzies Research Institute, Hobart, Tasmania and Royal North Shore Hospital, Sydney, New South Wales). Participants will be recruited and randomly allocated to either high or low dose fish oil, following completion of a one month run-in period.

All participants will provide written informed consent. The study has been approved by The Queen Elizabeth Hospital, Royal North Shore Hospital and Tasmanian Human Research Ethics Committees. The trial was registered with the Australian New Zealand Clinical Trials Registry (ACTRN 12607000415404) on 19th August 2007.

The proposed flow of subjects through the study is shown in Figure 1.

Figure 1. Flow of subjects through the FOSTAR study

RECRUITMENT

Subjects will be recruited at three centres through patient databases currently held by study

Investigators and direct advertising in local newspapers and Arthritis Australia newsletters.

INCLUSION CRITERIA

The inclusion criteria required (i) age greater than 40 years (ii) clinical knee OA defined using American College of Rheumatology criteria [1] and (iii) VAS knee specific pain score greater than 20mm (0-100mm scale). The knee which is most symptomatic knee, as determined by the participant, will represent the ‘index’ knee for the remainder of the study.

EXCLUSION CRITERIA

Exclusion criteria included (i) dementia or inability to give informed consent, (ii) pregnancy or lactation, (iii) severe knee OA (Grade 3 radiographic joint space narrowing using the Osteoarthritis Research Society International atlas), (iv) planned knee replacement surgery, (v) long-term use (≥ 6 months) of anti-inflammatory dose of fish oil (15mL of oil or ≥ 9 capsules), (vi) presence of inflammatory arthritis and (vii) contra-indications to MRI.

RUN-IN PERIOD

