High dose fish oil contains EPA 18% and DHA 12%, supplying 4.5g EPA+DHA per day. The low dose comparator oil, a blend of fish oil and high oleic sunola oil in a ratio of 1:9, supplies 0.45g EPA + DHA per day, which is equivalent to 1.5 standard 1g fish oil capsule daily. Both oils are flavoured with citrus oils and will be provided in identical dark 500mL bottles. Fish oil is sourced from Berg LipidTech Aalesund, Norway. The oils, blending, masking and bottling is performed by Melrose Health, Victoria, Australia. Study oil bottles will be returned at each study visit and volume of unconsumed oil measured to assess compliance. The presence of fish oil in the comparator will obviate the ethical problem of denying patients n-3 fatty acids that are recommended for cardiovascular health and will also add 'fishy' sensate properties that will militate against unmasking. We have previously shown addition of citrus flavouring to fish oils and vegetable oils achieves masking. The EPA and

DHA dose in the undiluted test fish oil has been shown to have anti-inflammatory effects in a variety of clinical settings, whereas the comparator oil will deliver a dose of fish oil that is well below the minimum amount (10ml/d) that has been associated with anti-inflammatory effects in RCTs. Participants will be provided with paracetamol (500mg) tablets with instructions that they could safely use up to 8 per day.

Participants will undergo assessments at baseline, 6 weeks, 3, 6, 9, 12, 18 and 24 months with interim phone calls to participants to encourage continuing compliance and participation

Dietary and general advice:

Subjects will be instructed to use olive oil based products (spreads, cooking oils, dressings etc), where possible, to minimise variation in consumption of n6 polyunsaturated fatty acids which compete with dietary n3 fatty acids. Written instructions regarding technique for taking the oil and directions for the background diet will be provided. All participants will also be given written information on knee osteoarthritis and generic instructions regarding exercises appropriate for maintaining knee function in OA and general fitness. The package of informed consent and written advice will include information regarding potential unwanted effects of fish oil and paracetamol.

COMPLIANCE

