Bone marrow lesions (BMLs) will be assessed on a proton density-weighted fat saturation 2D fast spin echo sequence in the sagittal plane. They will be defined as areas of increased signal adjacent to the subcortical bone at the medial tibial, medial femoral, lateral tibial, lateral femoral, superior patella and inferior patella sites. One trained and blinded observer will score BMLs by measuring the maximum area of the lesion (mm^2) at baseline and follow-up, as previously described [8]. The intraclass correlation coefficient (ICC) in our hands for this method of measurement is 0.97 [8].

Radiographic assessment:

Radiographs will only be used as a screening tool at participant recruitment, and not as an outcome measure. Radiographs of the index knee in the Buckland-Wright view will be taken at baseline, to allow comparison with MRI assessments and as this is putatively the most reproducible technique with regard to non-fluoroscopic positioning [9].

Radiographs will be scored independently by 2 trained observers at each site using a published atlas to classify disease in the tibiofemoral joint. The radiographic features of tibiofemoral

OA will be graded in each compartment on a 4-point scale (0-3) for individual features of osteophytes and joint space narrowing [10]. We have shown previously high degrees of intra-observer and inter-observer reproducibility for agreement on features of OA in the knee with regard to both osteophytes and joint space narrowing [11].

Success of Blinding:

Success of blinding will be assessed by asking the participants the following question:
“If you were asked which oil you were taking during the FOSTAR study would you say? Possible responses: Low dose, comparison oil OR high dose fish oil OR I am not sure which oil I may have been taking”. This will be asked at final visit.

ANALYSIS PLAN

Both intention-to-treat and per protocol analyses will be undertaken. Multiple imputation will be used for missing data. Analyses will be performed using longitudinal mixed model regression. The primary interpretation will be the comparison between the two treatment groups at the end of study.

SAMPLE SIZE CONSIDERATION

Sample sizes of 100 per treatment group were selected based on power calculations for longitudinal (ie repeated data) data with 6 treatment visits, $\alpha = 0.05$, $\beta = 0.2$, an attrition rate of 5% per visit, and a standardised treatment effect at the end of the study of 0.4 (i.e. a medium effect).

WITHDRAWALS

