Does the subject suffer from dementia or be unable to give informed consent?	
Is the subject pregnant or breastfeeding, or is she unable or unwilling to use an adequate method of contraception?	 
Does the subject have Grade – 4 changes in their knee which is to be investigated	 
Has the subject ingested $\geq 10\text{mL}$ or ≥ 9 standard capsules of fish oil daily for the proceeding 3 months	 
Does the subject have any contra-indications for having MRIs or DEXA scans performed?	 
Does the subject have any clinically significant condition(s) such as (but not limited to) cancer, rheumatoid arthritis, psoratic arthritis, lupus or fibromyalgia? that in the opinion of the investigator may compromise their safety or compliance, interfere with evaluation or preclude completion of the study	 
A tick recorded in any of the shaded boxes above signifies that the subject is ineligible and should be excluded from entering the study	

ENROLMENT CODE

If ALL inclusion and NO exclusion criteria have been met, the study subject may be assigned an enrolment code:

E

PHYSICAL EXAMINATION/VITAL SIGNS	
Height	cms
Weight	kgs
Blood Pressure	mmHG

Site Number:

Randomisation Number:

Subject Initials:

Study Selected Knee:

RUN-IN FISH OIL		
	YES	NO
Has the run-in fish oil been supplied and explained?		
Has the dosing DVD been shown to the subject?		
Has the first dose of fish oil been taken under supervision in the clinic?		

PREVIOUS FISH OIL USE		
	YES	NO
Have you ever used fish oil prior to your involvement in this study?		
If yes, what was your average daily consumption of fish oil? Where 1 capsule OR 1 mL of liquid fish oil = 1gg/day	

[figure not shown]
PREPARATION FOR NEXT APPOINTMENT		
	YES	NO
Has a baseline/randomisation appointment been made?		
Has the subject been booked in for fasting blood tests prior to randomisation visit?		

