Does the subject meet inclusion criteria of: 
1. Less than Grade – 4 changes in their study selected knee2. An osteophyte on x-ray3. At least one of the following:
- knee age greater than 50 years- stiffness lasting less than 30 minutes4. crepitus		
A tick recorded in any of the shaded boxes above signifies that the subject is ineligible and should be excluded from entering the study		

RANDOMISATION CODE
If ALL inclusion criteria have been met, the study subject may be assigned a randomisation code:
R       

Site Number:

Randomisation Number:

Subject Initials:

Study Selected Knee:

MEDICAL CHANGES		
Has the subject been diagnosed with any NEW medical conditions since their last visit?		
NEW MEDICAL CONDITION	Date of Onset (DD/MM/YYYY)	Date Resolved Or √ Ongoing (DD/MM/YYYY)
		
		
		
If the subject is currently taking any medications for any of the above conditions, ensure that details are recorded in the Concomitant Medications record .		

CONCOMITANT MEDICATIONS					
Has the subject started, stopped or changed the doses of any medications since their last visit? (Ask to see all medications used)					
Brand Name	Dose (4)	Units (mg)	Route (po)	Start/Stop Dates (DD/MM/YYYY)	Ongoing
				Start...../...../..... Stop...../.../.....	
				Start...../...../..... Stop...../.../.....	
				Start...../...../..... Stop...../.../.....	
				Start...../...../..... Stop...../.../.....	
Please remember to transfer any details here to concomitant medications page					

HOSPITALISATIONS/DAY PROCEDURES			
Has the subject been to hospital for any medical procedures since their last visit?			
 YES  NO			
If Yes, please provide details below			
Date Admitted DD/MM/YYYY	Date Discharged DD/MM/YYYY	Doctor's Details	Purpose

Site Number:

Randomisation Number:

Subject Initials:

Study Selected Knee:

Total Number of Hospitalisations since last visit:			

KNEE OSTEOARTHRITIS HISTORY	
With regard to the pain in your study-selected knee ;	
How long have you experienced pain in that knee?years

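### The eligibility forms use a Grade 4 cut-off on no named scale, while the protocol excludes Grade 3 narrowing on a 0-3 scale; three other form items also depart from the protocol

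*Supplement*

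**What the plan says.** **Protocol.** The Exclusion Criteria section bars, as item (iii), "severe knee OA (Grade 3 radiographic joint space narrowing using the Osteoarthritis Research Society International atlas". The Radiographic assessment section gives the scale: "OA will be graded in each compartment on a 4-point scale (0-3) for individual features of osteophytes and joint space narrowing". It also gives the purpose of the films: "Radiographs will only be used as a screening tool at participant recruitment, and not as an outcome measure". Item (iv) bars planned knee replacement. Item (v) bars "long-term use (≥ 6 months) of anti-inflammatory dose of fish oil (15mL of oil or ≥ 9 capsules".

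**Forms (Appendix 1).** The Visit 1 exclusion list asks "Does the subject have Grade – 4 changes in their knee which is to be investigated". At Visit 2 the Knee X-ray block requires "Less than Grade – 4 changes in their study selected knee", and the inclusion list just before the randomisation code repeats the requirement. The Visit 1 fish-oil exclusion asks about 10 mL or more, or at least "9 standard capsules of fish oil daily for the proceeding 3 months". The question on investigational drug use within 30 days of screening stands in the Visit 1 inclusion list.

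The forms control entry. An enrolment code may be assigned when every inclusion criterion and no exclusion criterion is met. A randomisation code may be assigned when every Visit 2 inclusion criterion is met.

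**The concern.** Staff assign codes from the form, so the form's rule decides who is randomised. A cut-off of Grade 4 does not fit a scale that stops at 3, and no form item mentions narrowing, an atlas or Grade 3. The protocol says the radiographs exist only for screening, so a mismatch here defeats their one stated use.

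The trial population and the cartilage outcome are at stake. Change in cartilage volume at two years is a primary outcome. The protocol keeps out knees with the most severe narrowing and knees already planned for replacement, and the forms as printed reliably enforce neither exclusion. If the index knee were replaced, its two-year cartilage volume could not be measured. Three centres reading an unlabelled grade may also apply it differently.

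The other departures concern the same checklists. A person can be eligible under the protocol's fish-oil rule and not under the form's, or the reverse. Read literally, the placement of the investigational-drug question makes recent use a condition of entry.

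**Working it through.** No sample-size or power figure bears on this point. The check is to set the rules side by side.

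**1. Radiographic grade.** Inputs: the scale and exclusion (iii) from the protocol body; the three form items from Appendix 1.

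- Grades on the protocol's scale: S = {0, 1, 2, 3}
- Barred by the protocol (narrowing): P = {3}
- Barred by the Visit 1 form: F = {4}
- Admitted by both Visit 2 items: A = {grades below 4}

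Results on the protocol's scale:

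- F ∩ S is empty, so the Visit 1 item bars no knee.
- A ∩ S = {0, 1, 2, 3}, so both Visit 2 items admit every knee.
- P ∩ (A ∩ S) = {3}, so the grade the protocol bars passes all three items.

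**2. Other readings of the form's grade.**

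- *A different grading system that has a grade 4.* The items would then bar some knees, but the documents neither name such a system nor map it to Grade 3 narrowing. Which protocol-barred knees would pass is unknown.
- *The fourth point of the 4-point scale.* Counting 0, 1, 2, 3, the fourth point is 3. The form, however, speaks of changes in general, and the scale covers osteophytes as well as narrowing, so the rule would still not be the protocol's unless the feature were named.
- *A character lost at the dash.* This cannot be ruled out from the text, but the same form appears three times, and the Visit 2 wording reads naturally as a plain Grade 4 limit.

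None of these readings is stated in the documents.

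**3. Prior fish oil.** I read the protocol's 15 mL as a daily amount of at least 15 mL. The protocol does not say how recent the use must be.

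| Case | Protocol item (v) | Visit 1 form |
|---|---|---|
| 15 mL daily for the last 6 months | Excluded | Excluded (15 ≥ 10; 6 ≥ 3) |
| 10 mL daily for the last 6 months | Not excluded (10 < 15) | Excluded (10 ≥ 10) |
| 15 mL daily for the last 3 months only | Not excluded (3 < 6) | Excluded (3 ≥ 3) |
| 15 mL daily for 6 months, stopped more than 3 months ago | Excluded if past use counts | Not excluded |

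The 9-capsule figure is common to both rules; the volume and the duration differ. The protocol's Intervention section describes the comparator as "well below the minimum amount (10ml/d) that has been associated with anti-inflammatory effects in RCTs". That figure matches the form's volume and not the volume in item (v).

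**4. Planned replacement.** Neither the Visit 1 nor the Visit 2 eligibility list has an item for exclusion (iv).

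**5. Investigational drug.** The question is in a list where all criteria must be met. I rely on its placement and on that rule. The box shading is not reliably shown in the available text.

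**The case against.** The best defence is that the form names no scale, so placing its Grade 4 on the 0-3 atlas scale is the reader's step. Under another system, or the loose fourth-point reading, the items would remove some severe knees. This stands as a limit: a reader might infer that the forms screen out no severe knee at all, and the documents support that only on the one scale they define. It does not rescue the forms, because an unnamed, unmapped grade is still a different rule from the protocol's.

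Second, the forms are not the only check. Two trained observers at each site score the films with an atlas, and the Visit 2 form refers to assessment by the principal investigator where no film was available at Visit 1. Sites could apply Grade 3 outside the form. So a reader might infer that Grade 3 knees were in fact enrolled, and nothing here shows that. Still, no form item asks for the observers' narrowing grade or compares it with the exclusion.

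Third, the lesser items are softer than they look. For current users the form's fish-oil rule is the stricter one; only past long-term users can slip through. The Visit 1 item on clinically significant conditions that may preclude completion gives partial, discretionary cover for planned replacement. Both points stand.

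Fourth, a reader might infer that replacement of the knee removes both primary outcomes. The Withdrawals section follows all participants for two years unless consent is withdrawn, so WOMAC pain could still be collected, though it would be harder to interpret. Only the cartilage measurement in that knee would be lost.

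**Conclusion.** The plan is wrong as written on this point. All three radiographic items on the forms differ from the protocol's exclusion. On the scale the protocol defines, they bar none of the four grades where the protocol bars one. On any other reading, the rule is undefined. The missing replacement item, the differing fish-oil rules and the misplaced drug question are real but smaller inconsistencies in the same checklists.

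The conclusion rests on the forms as printed and on their stated role in assigning codes. It concerns what the forms permit.

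The number of participants affected cannot be computed, because no grade distribution is given. A reader might also infer that the standardised effect of 0.4 in the Sample Size Consideration section would be diluted by the share of Grade 3 knees. The documents do not support this. That 0.4 belongs to a calculation for repeated data over six treatment visits, whereas MRI is done only at baseline and two years. No text says that Grade 3 knees would show no effect, and narrowing is graded by compartment while cartilage is measured in separate plates.

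**What to change.** Reconcile the protocol and the forms:

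1. Make the Visit 1 exclusion item and both Visit 2 items state the same scale, radiographic feature and cut-off as the protocol exclusion. Do not add a compartment rule on the form alone; exclusion (iii) contains none. Which cut-off is clinically right is for the investigators, but there must be one.
2. Add an item for planned knee replacement.
3. Use one prior-fish-oil amount and duration in both places, and say whether past use counts.
4. Move the investigational-drug question to the exclusions.

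If participants have already entered on these forms, compare their recorded narrowing grades with exclusion (iii) and report any departures.

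The cost is a few revised form pages and a notice to the three centres. Some knees that the forms now admit would no longer be enrolled if the protocol's exclusion is kept, as the protocol already intends.

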DD/MM/YYYY									
Yes No									
Has a copy been provided to the subject for their records  									
Has a copy been added to the subjects hospital records 									
									
Has the original been filed in the subjects CRF  									

DEMOGRAPHICS									
Date of Birth   /   /    									
DD/MM/YYYY									
Gender									
 Female									
 Male									

Site Number:

Randomisation Number:

Subject Initials:

Study Selected Knee:

Ethnic Origin

- Caucasian
- Asian
- Hispanic
- Other (specify below)

SURGICAL HISTORY	
Previous Surgical Procedures	Date of Procedure (DD/MM/YYYY)

If the subject is currently taking any medications for any of the above procedures, ensure that details are recorded in the Concomitant Medications record.

CO-MORBIDITIES				
Have you ever been told by a Dr or a nurse that you have any of the following conditions?		If yes, Do you currently have these conditions?		
	YES	NO	YES	NO
Diabetes				
Osteoporosis				
High Blood Pressure				
Asthma				

Site Number:

Randomisation Number:

Subject Initials:

Study Selected Knee:

Bronchitis				
Emphysema/Chronic bronchitis				
Stroke				
Heart Attack				
Angina				
High Cholesterol				

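### The forms that release the enrolment and randomisation codes do not carry two of the protocol's exclusions: planned knee replacement is absent and inflammatory arthritis is left to the investigator's opinion

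*Supplement*

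**What the plan says.** The Exclusion Criteria section of the protocol lists seven exclusions. The fourth is "iv) planned knee replacement surgery" and the sixth is "vi) presence of inflammatory arthritis". Neither has a condition attached or leaves room for judgement.

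Appendix 1 holds the forms that sites complete. The Visit 1 form has its own exclusion list, followed by the rule for issuing a code: "If ALL inclusion and NO exclusion criteria have been met, the study subject may be assigned an enrolment code". Inflammatory arthritis appears there only within an item on "clinically significant condition(s) such as (but not limited to) cancer, rheumatoid arthritis, psoratic arthritis, lupus or fibromyalgia", which is qualified by "that in the opinion of the investigator may compromise their safety or compliance, interfere with evaluation or preclude completion of the study". The surgical section of that form is headed "Previous Surgical Procedures".

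The Visit 2 form gives the next release rule: "If ALL inclusion criteria have been met, the study subject may be assigned a randomisation code". Both assessment schedules (Table 1 in the protocol body and the one opening Appendix 1) mark inclusion and exclusion criteria for checking at Visit 1 and again at Visit 2.

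**The concern.** In daily use the form is the gate. It tells the coordinator when a code may be issued, and three centres would work from it. If the form omits a criterion or softens it, a site can complete every box properly and still admit someone the protocol excludes.

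The two exclusions concerned bear on the primary outcomes. Both outcomes, WOMAC pain and MRI cartilage volume, relate to the knee, and the Analysis Plan bases its primary interpretation on the end-of-study comparison. If the index knee is replaced before month 24, there is no native cartilage to measure at 2 years. Because the Withdrawals section follows everyone for two years, a pain score would still be collected at month 24, but it would describe a replaced knee. The Analysis Plan does not say how such a value is to be handled. Participants with inflammatory arthritis have a second source of joint symptoms, so their inclusion blurs the population to which an osteoarthritis result applies.

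**Working it through.** The check is a comparison of texts. The seven protocol exclusions against the Visit 1 list:

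| Protocol exclusion | Visit 1 form |
|---|---|
| (i) dementia or inability to consent | item present |
| (ii) pregnancy or lactation | item present, with contraception added |
| (iii) severe radiographic disease | item present, worded differently |
| (iv) planned knee replacement | **no item** |
| (v) long-term fish oil use | item present, worded differently |
| (vi) inflammatory arthritis, presence sufficient | **only as examples in an item subject to the investigator's opinion** |
| (vii) contra-indications to MRI | item present, with DEXA added |

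The differences in (iii) and (v) are outside this point. A row with two empty boxes stands before the dementia item, across a page break. That item shows only one box of its own, so the row is probably its displaced boxes and not a lost criterion.

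**Could another Visit 1 field catch (iv)?** The surgical history asks about past procedures. None of the inclusion items concerns surgery.

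**Does Visit 2 close the gap?** Its list covers run-in oil consumption, pain, continued consent and the X-ray features. It has no exclusion items. The questions there on hospital procedures and on earlier surgery to the knee look backward, and they come after the randomisation-code box.

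**Does the opinion clause govern the arthritis examples?** A stray question mark stands before the clause, but the clause makes sense only as a qualifier of that item.

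**Size.** The documents give no rate of planned replacement, so what follows is illustration on an assumed range.

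- The plan's own figure comes first. With effect 0.4 SD, alpha 0.05 (two-sided assumed) and power 0.80, n per arm = 2 × (1.96 + 0.842)² / 0.4² ≈ 98.1, rounded up to 99. This is close to the stated 100 without attrition. Simple two-sample power at 100 per arm is 0.807.
- The plan's method is longitudinal, with 5% attrition per visit over 6 visits, but the within-person correlation is not given. A mixed-model calculation with an effect growing linearly to 0.4 and an equal correlation between visits of 0.3, 0.4 or 0.5 gives power of 0.74, 0.80 or 0.86. So 100 per arm is attainable on the stated design, and it is not in dispute here.
- Planned attrition leaves 0.95⁶ = 0.735, or 200 × 0.735 = 147 at the end.
- Suppose that 2% to 10% of those enrolled had the index knee replaced before month 24. Then 4 to 20 people would lose the 2-year cartilage measure. Applying the same attrition to the rest leaves 196 × 0.735 = 144 down to 180 × 0.735 = 132.
- Simple two-sample power, before other attrition, would go from 0.807 to 0.800 (2%), 0.787 (5%) or 0.765 (10%).

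**The case against.** The strongest reply is that the design itself is right. The protocol excludes both groups outright and still binds the sites, so enrolling such a person would be a protocol deviation. The Visit 1 release rule speaks of exclusion criteria in general, which can be read to include the protocol's own list. The open-ended item could also catch someone listed for surgery, because it mentions interference with evaluation and failure to complete. The two named arthritides at least prompt the question.

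Much of this stands. The fault is a form that does not mirror a sound protocol. Three things remain. The sentence just before the Visit 1 code box ties ineligibility to ticks in the boxes above it, so the list on the form is the natural reference. The Visit 2 rule mentions inclusion criteria only, so the wider reading is not available there. The open-ended item asks about conditions, not planned operations, and it is discretionary.

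A reader might also infer more than the documents support:

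- *That these participants' primary outcomes will be lost.* Protocol (iv) is not limited to the index knee, and replacing the other knee leaves index-knee cartilage measurable. Pain is measured at 3, 6, 9, 12 and 24 months and analysed with a longitudinal mixed model, so visits before surgery still contribute.
- *That the treatment comparison would be biased.* Surgery planned before randomisation is a baseline characteristic, balanced between arms in expectation. The documents give no mechanism for a difference between arms.
- *That a benefit acting through inflammatory arthritis would be mistaken for an osteoarthritis effect.* The Intervention section refers to anti-inflammatory effects in various clinical settings without naming that disease. A few such participants would change the population studied, not the validity of the randomised comparison.

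**Conclusion.** The mismatch is real and rests on the text alone. Two unconditional exclusions are not enforced by the forms that release the codes: one has no item and the other is discretionary. A site relying on the forms could randomise people the protocol excludes. This is an inconsistency between protocol and forms, not a fault in the choice of population.

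The expected consequence is modest: some loss of precision and interpretability at 24 months, through replaced index knees and a less clearly defined osteoarthritis population. Its size cannot be derived from the documents. The 2% to 10% illustration assumes that every such person passes screening unnoticed and has the index knee replaced before month 24. It also adds that loss to the planned 5% per visit, which may already include surgical losses. Even on those terms, simple power falls at most from 0.807 to 0.765. No figure can be attached to the inflammatory-arthritis part. The text comparison supports high confidence in the mismatch, but not in any particular amount of lost data.

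**What to change.** Reconcile the Appendix 1 forms with the protocol's Exclusion Criteria:

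- At Visit 1, add a yes/no item on planned knee replacement, and a separate yes/no item on inflammatory arthritis with no reference to the investigator's opinion.
- At Visit 2, repeat both items before the randomisation code. Reword the release rule so that it requires no exclusion to be present, in line with the two schedules.
- Keep the investigator-opinion item for other conditions only.

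The cost is two tick-box items at each of two existing visits, with no new procedure. There may be a few more screening failures, all of them people the protocol already excludes.
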